6 EFFICACY VARIABLES AND ANALYSES

The analyses of efficacy endpoints will be performed using the FAS. Efficacy data described below will be listed using the FAS.

6.1 Primary endpoint analysis

The time windows used for the primary endpoint analysis will follow the definition provided in Section 11.7.

6.1.1 Primary efficacy endpoint

The primary efficacy endpoint of this study is defined as the change from baseline to Week 12 in the number of BE days per week based on diary data.

A 'BE day' is a day in which at least one confirmed BE episode occurred.

The number of BE days per week will be calculated based on 2-week (rather than 1-week) intervals in order to improve the precision of the variable, as shown by simulations. A minimum of 7 diary entries per 14-day time interval is required, otherwise the number of BE days will be considered missing.

The number of BE days per week is defined as the number of diary days with at least one BE episode during the applicable 14-day time interval divided by the total number of diary days, times 7. A diary day is a day for which the number of BE episodes is entered in the study participant's diary (this includes a zero value, i.e., no BE episode).

6.1.2 Overall testing strategy

The H_0 to be tested is that there is no difference between ACT-539313 and placebo with respect to the primary efficacy endpoint:

H₀: $\mu_A = \mu_P \text{ vs } H_a$: $\mu_A \neq \mu_P$

Here, μ_A and μ_P is the mean change from baseline to Week 12 in the number of BE days per week in the ACT-539313 and placebo group, respectively. The null hypothesis will be tested at a two-sided 0.05 significance level.

A preview of the main analyses is given in Table 3 using the estimand terminology [ICH 2020]. Estimands are defined by five attributes: treatment condition of interest, target population, endpoint, strategy for addressing intercurrent events (i.e., premature discontinuation of treatment or use of other, forbidden, medication for BE), and population-level summary. The primary estimand is based on the primary endpoint. A supplementary estimand is obtained by changing one or more attributes. For both estimands the treatment condition is ACT-539313 b.i.d. for up to 12 weeks, whereas the alternative condition is placebo b.i.d. for the same period. The other four attributes are given in Table 3. Differences vs the primary estimand are indicated in *bold italics*.

Table 3	Estimands for the	primary objective	e	
Estimand	Target Population	Endpoint	Strategy for addressing intercurrent events	Population- level summary
Primary Estimand	Adult study participants with BED according to DSM-5, having at least 3 BE days per week at baseline.	Change from baseline to Week 12 in the number of BE days per week	Hypothetical, i.e., endpoint data after intercurrent event are not used.	Mean change from baseline to Week 12 for each treatment group. Treatment effect
				expressed as difference of LSMean changes from baseline to Week 12 (ACT-539313 minus placebo; from mixed model)
Supplementary Estimand #1	participants with BED according to DSM-5, having at least 3 BE days per	Change from baseline to Week 12 in the number of BE episodes per week	Hypothetical, i.e., endpoint data after intercurrent event are not used.	Mean change from baseline to Week 12 for each treatment group.
	week at baseline.			Treatment effect expressed as difference of LSMean changes from baseline to Week 12 (ACT-539313 minus placebo; from mixed model)

ACT-539313 ID-082A201 1 April 2022, page	22/60	Confidential		istical Analysis Plan linical Study Report Version 3 Doc No D-22.100
Estimand	Target Population	Endpoint	Strategy for addressing intercurrent events	Population- level summary
Supplementary Estimand #2	Adult study participants with BED according to DSM-5, having at least 3 BE days per	Change from baseline to Week 12 in the number of BE days per week	Hypothetical, i.e., endpoint data after intercurrent event are not used.	Mean change from baseline to Week 12 for each treatment group.

Treatment effect

completing expressed as 12 weeks of difference of treatment LSMean without use of changes from other baseline to medication Week 12 (ACT-539313 minus placebo; from mixed model)

week at baseline,

Intercurrent events are premature discontinuation of treatment and use of other, forbidden, medication for BE.

BE = binge eating; BED = binge eating disorder; DSM-5 = Diagnostic and Statistical Manual of Mental Disorders (5th edition); LSMeans = Least Squares Means.

In the choice of intercurrent events it was considered that, in symptomatic settings, it is not the usual practice to continue to assess effectiveness in subjects after they have stopped taking the assigned treatment [O'Neill 2012]. Also, if an alternative (or additional) drug is started, this could influence the outcome for a subject [O'Neill 2012]. Therefore, two types of intercurrent events were considered: premature discontinuation of double-blind treatment (ACT-539313 or placebo) and use of other forbidden medication for BE.

Excluding measurements obtained after an intercurrent event will lead to a hypothetical strategy estimand (ICH E9[R1]). A hypothetical strategy is related to the scenario in which the intercurrent events would not occur (i.e., all subjects completing the 12 weeks of assigned treatment without using forbidden BE medication), which is a reasonable approach for this proof-of-concept study.

6.1.3 Statistical model

A linear mixed effects model will be used for the analysis of change from baseline in the number of BE days per week.

The analysis model will include the baseline number of BE days per week, treatment group (ACT-539313; placebo), sex, BMI category (< 30; ≥ 30 kg/m²), time point (Weeks 1–2;

ACT-539313		Statistical Analysis Plan
ID-082A201	Confidential	for Clinical Study Report
1 April 2022, page 23/60	Confidential	Version 3
		Doc No D-22,100

3-4; 5-6; 7-8; 9-10; 11-12), and the interaction of treatment by time point and baseline by time point.

An unstructured covariance matrix will be used to model the correlation among repeated measurements. A restricted maximum likelihood approach in combination with the Newton Raphson Algorithm will be used to derive (unbiased) estimates of variance components. The Kenward-Roger approximation will be used to compute the denominator degrees of freedom and adjust standard errors [Kenward 1997]. If the analysis fails to converge, the following structures will be tested in a subsequent order until model-convergence is achieved: heterogeneous Toeplitz; Toeplitz; autoregressive; compound symmetry. A sandwich estimator will be used to address the potential misspecification of the aforementioned structured covariance matrixes.

To test the null hypothesis (H_0), appropriate contrasts will be used to test the treatment difference of interest (i.e., the difference in least squares [LS] mean change from baseline between ACT-539313 vs placebo at Week 12) [see Section 14.1].

The LSMean for each treatment group per time point will be displayed along with associated standard errors and 95% CIs. For the ACT-539313 comparison with placebo, the placebo-adjusted LSMean will be displayed along with associated standard error, 95% CI and unadjusted two-sided p-value. The null hypothesis will be rejected if the 95% CI around this difference excludes zero.

6.1.3.1 Model diagnostic and checks for normality

In order to assess the normality assumption of the MMRM, QQ-Plots and histograms (including an overlay of a normal density curve) of the studentized residuals, and figures comparing the studentized residuals versus the predicted residuals will be produced.

If the normality assumption does not hold, the primary endpoint will be analyzed using a non-parametric rank analysis of covariance [Quade 1967, Koch 1982, Koch 2016, Stokes 2012] adjusted for the baseline value as follows:

- 1. Produce standardized ranks for the baseline value (covariate) and the change from baseline to Week 12 variable (response).
- 2. Fit a linear regression model with the standardized ranks of the baseline variable and the change from baseline to Week 12 variable as independent and dependent variable, respectively. Retain the regression residuals.
- 3. Apply the Cochran-Mantel-Haenszel mean score test using the residuals as scores to compare treatment groups. The p-value from this test will be used to test the null hypothesis.

The rank analysis of covariance does not provide an interpretable treatment effect estimate. Therefore, the magnitude of the treatment effect will be estimated using the unadjusted

ACT-539313		Statistical Analysis Plan
ID-082A201	Confidential	for Clinical Study Report
1 April 2022, page 24/60	Confidential	Version 3
		Doc No D-22.100

non-parametric win ratio [Wang 2016] between ACT-539313 and placebo with corresponding 95% CI, derived via bootstrap (10,000 samples) using the bias-corrected method [Carpenter 2000] on the log-transformed win ratio. The rejection of the null hypothesis will be solely based on the p-value from the rank analysis of covariance and not the 95% CI of the unadjusted win ratio estimator.

All study participants with a valid value for the change from baseline to Week 12 will be ranked based on these values (such that larger decreases are associated with better ranks). Study participants with a missing value for the change from baseline to Week 12 will be assigned worse ranks than study participants with available change from baseline to Week 12 values based on their last available change from baseline value prior to Week 12. Study participants with a non-missing baseline value but no post-baseline data will be excluded from the analysis. Mid-ranks are used in the event of ties.

6.1.4 Handling of partially missing data

Partially missing data refers to some missing entries in the BE diary that should be filled in daily.

Partially missing data for the BE diary will be handled as follows: a minimum of 7 days of entries per 14-day time interval is required; otherwise, the mean value will be considered missing for that time point.

This approach uses implicit imputation: missing data points are given the same value as the mean of the non-missing data points of that same time point or week.

The (partially) missing data patterns of the primary efficacy endpoint will be shown with a shift table for each treatment group. The table will show the shifts in the number of available BE values (categorized as < 7, 7-10, 11-14 days) from baseline to Week 3–4, Week 7–8, and Week 11–12 (Week 1–2, Week 5–6 and Week 9–10 will be available in the listing).

6.1.5 Descriptive statistics

The primary efficacy endpoint along with its observed values (i.e., bi-weekly averages of BE episodes; see Table 6) will be summarized using descriptive statistics.

A plot of the mean (\pm SE) change from baseline over time (per weeks, as defined in Table 6) for the number of BE days by treatment group will be provided together with a summary table.

The incidence and pattern of missing values will be explored to assess the appropriateness of the statistical analysis and possible impact on results. The incidence of missing data and the observed missing data patterns for the primary endpoint at Baseline and time point (Weeks 1–2; 3–4; 5–6; 7–8; 9–10; 11–12) will be presented for each treatment group. The

ACT-539313		Statistical Analysis Plan
ID-082A201	Confidential	for Clinical Study Report
1 April 2022, page 25/60	Confidential	Version 3
		Doc No D-22 100

missing data patterns will be sorted from completely missing to completely observed by the order of the first occurrence of missing data.

The mean change from baseline of the primary efficacy endpoint, for both study completers and for premature study withdrawals, will be plotted over time (Weeks 1–2; 3–4; 5–6; 7–8; 9–10; 11–12) and displayed in a summary table by treatment group. In case the percentage of study withdrawals will be above 15%, the reasons for study withdrawals will also be plotted.

The same plot and table will also be provided for study treatment completers and study treatment discontinuers.

Based on the exploration of the observed missing data patterns, further sensitivity analyses to those described below may be performed.

6.1.6 Sensitivity analyses

The linear mixed effects model (or MMRM) relies on the MAR assumption. That is, conditional on the statistical model and observed values of the outcome, the probability of missing data does not depend on the unobserved values of that outcome. Consequently, the study participant's missing values are estimated based on similar study participants who remain in the study. MAR is a common assumption for analyses associated with a hypothetical strategy estimand.

Sensitivity analyses will be performed to assess the robustness of the conclusions of the main analysis to departures from the MAR assumption. For this, a model that assumes MNAR will be used [Mallinckrodt 2013]. This model will be based on MI methodology [Rubin 1987] and will be specifically used to assess the bias that can result when the outcomes for participants who discontinue differ from those who complete. Sensitivity analyses will be performed for the analysis of the primary endpoint.

As a general approach, imputations will be performed on observed values (i.e., bi-weekly averages at Baseline, Weeks 1–2, 3–4, 5–6, 7–8, 9–10, 11–12) specifying a minimum and a maximum threshold. The change from baseline will not be imputed to avoid imputation of nonsensical values (e.g., an imputed change from baseline to Week 12 equal to -5 with a baseline of 4 would lead to an implicit imputed value of -1 for Week 12, which is not possible). The boundaries will range from 0 to 7.

When an intended imputed value is outside the defined boundaries, this value will be discarded, and the procedure will draw another value for imputation. The maximum number of discarded values will be set to 100 for each imputed dataset, i.e., an imputed dataset will not be generated if more than 100 values have been discarded (SAS will print an error message in the log: "*An imputed variable value is not in the specified range after 100 tries*"). If more than 20% of the planned imputed datasets are not produced, the results for that analysis will not be shown as this would likely lead to unreliable conclusions. Once

ACT-539313		Statistical Analysis Plan
ID-082A201	Confidential	for Clinical Study Report
1 April 2022, page 26/60	Confidential	Version 3
		Doc No D-22.100

all the multiply-imputed datasets are generated, the change from baseline to Week 12 will be calculated from the bi-weekly averages for each data set.

In all the MI analyses described below, a single preliminary step will be performed to obtain a monotone missing data pattern [see Section 11.6]. That is, any non-monotone (or intermediate) missing data of the bi-weekly averages will be imputed using the MCMC methodology [Schafer 1997] under MAR assumptions within each treatment group. This assumption is considered reasonable given that study participants could miss intermediate visits due to reasons unrelated to their BE disorder (e.g., scheduling conflicts or COVID-19). The MCMC imputation will be performed by treatment group, and the variables included in the model are: sex, BMI (continuous), baseline, and time point (Weeks 1–2, 3–4, 5–6, 7–8, 9–10, 11–12). The MCMC methodology assumes a multivariate normal distribution of these variables [see SAS[®] code in Section 14.2].

As a reference for the sensitivity analyses under MNAR (described below), the main analyses will be repeated using MI methodology under MAR. Imputation for monotone missing data will be performed sequentially, one time point at a time using the linear regression method [Ratitch 2013]. A linear regression model will be fitted sequentially for each time point (i.e., Weeks 1-2 and then Weeks 3-4, Weeks 5-6, Weeks 7-8, Weeks 9–10, Weeks 11–12) with treatment (ACT-539313; placebo), sex, BMI category, baseline, and any prior time point (e.g., Weeks 1–2 when fitting the linear regression model to Weeks 3–4 values and so on) as predictors. Missing values are then replaced for each visit sequentially (i.e., Weeks 1–2 and then Weeks 3–4, Weeks 5–6, Weeks 7–8, Weeks 9– 10, Weeks 11-12) by predictions from the respective linear regression model [Rubin 1987]. Note that values imputed at Weeks 1–2 are included when fitting the linear regression model to Weeks 3–4 values (the same approach will be implemented for the imputation of the other time points). The resulting multiple data sets are analyzed using the same statistical model as for the primary analysis (i.e., linear mixed effects model with the same factors). Results from these analyses are combined using Rubin's methodology [Rubin 1987]. The results obtained from this MI analysis are expected to be similar to the main MMRM analysis since both methods rely on the same MAR assumption.

A delta-adjusted imputation method will be used to progressively stress test the MAR assumption of the main analysis. That is, a tipping-point analysis will be performed to see how severe departures from the MAR assumption must be to overturn the conclusions of the main analysis (i.e., the point where significant results become non-significant). The assumption here is that study participants from the ACT-539313 group who discontinue from the study would have, on average, their observed efficacy score worsened by some amount (delta) compared with the efficacy observed from study participants of the same ACT-539313 group that remain in the study. A series of analyses with progressively increasing deltas ($\delta_{BE \ days \ per \ week} = 0.25$, 0.5, 0.75, 1, 1.25, 1.5, 1.75, 2; from less conservative to more conservative) will be performed. The delta adjustment will only be made to the multiply-imputed values (based on the MAR assumption) for the subjects in the ACT-539313 group. Note that a delta of zero corresponds to the standard MAR-based MI analysis that is described above to obtain a reference for the sensitivity analyses. Again, the same linear mixed effects model as in the main analysis will be used.

For all the analyses described above which use MI methodology, 100 multiply-imputed datasets are created. The decision to impute 100 datasets was based on O'Kelly [O'Kelly 2014], where it is stated that the number of imputations should typically be between 20 and 100 [Graham 2007]. Similar recommendations have also been provided by other authors [Bodner 2008, Von Hippel 2009, White 2011].

For each planned sensitivity analysis, the LSMean estimate of the difference in change from baseline between ACT-539313 vs placebo at Week 12 will be provided, together with its estimated standard error and associated p-value. The LSMean estimate of the change from baseline for each treatment group at Week 12 will also be provided, together with its estimated standard error and associated p-value.

A plot over time for the primary efficacy endpoint showing the LSMean of each treatment group per imputation method (i.e., MAR; J2R; delta-adjusted including $\delta = 0$) will be provided.

ACT-539313		Statistical Analysis Plan
ID-082A201	Confidential	for Clinical Study Report
1 April 2022, page 28/60	Confidential	Version 3
		Doc No D-22.100

Any missing diary data due to the COVID-19 pandemic is considered missing completely at random and satisfies the assumption underlying the main analysis (linear mixed-effects model, assuming missing at random). Nevertheless, efforts will be made to retain study participants in the trial and adhere to the schedule of assessments. Visits are performed at regular and short intervals for the investigator to closely follow-up with the diary completion. The COVID-19 pandemic may lead to missed or postponed visits, but the study participant's BE diary can still be evaluated at the next visit to collect the information for the primary endpoint. In addition, the study protocol accounts for remote visits in case study participants cannot, are not allowed to, or are not willing to travel to the investigator's site because of the COVID-19 pandemic. The paper-based BE diary, used to assess the primary endpoint, will be filled in by the study participants at home and subsequently reviewed by the investigator during the clinic visits. If in-person visits will be not possible because of the COVID-19 pandemic, the data will be reviewed remotely via a telephone call or a video call; delivery of BE diary booklets and/or study treatment to the trial participants' home is also foreseen under such circumstances.

6.1.7 Supportive analyses

The main analysis performed for the primary efficacy endpoint [Section 6.1.3] will be repeated using the PPS to assess the effect protocol deviations may have on the results.

In addition, the main analysis performed for the primary efficacy endpoint [Section 6.1.3] will be repeated considering all data collected to evaluate the effect intercurrent events may have on the results (see Section 14.12 for the list of BE forbidden medications).

6.1.8 Subgroup analyses

Subgroup analyses for the primary efficacy endpoint will be performed to investigate the consistency of the treatment effect (i.e., ACT-539313 vs placebo) across subgroups defined by:

Age:	18-29, 30-55 years
Sex:	Male, female
Race:	Black, White, other
BMI:	$< 30, \ge 30 \text{ kg/m}^2$

Treatment effect estimates (LS Means) and their 95% CIs (obtained by conducting the primary analysis by subgroup) will be presented as forest plots with vertical reference lines at 'no effect' as well as at the 'overall treatment effect'. P-values for treatment by subgroup interaction will be provided for exploratory purposes, based on the primary analysis model extended with treatment by time and by subgroup interaction.

6.2 Secondary endpoint analysis

Not applicable.

ACT-539313		Statistical Analysis Plan
ID-082A201	Confidential	for Clinical Study Report
1 April 2022, page 29/60	Confidential	Version 3
		Doc No D-22.100

6.3 Analysis of exploratory efficacy variables

The following efficacy endpoints will be summarized using descriptive statistics:

- Change from baseline up to Week 12 (EOT) in the number of BE episodes per week^a.
- Absence of BE episodes ('Yes'^b/'No') during the last 4 weeks of the treatment period^c.
- Change from baseline to Week 12 (EOT) in the total score of the YBOCS-BE.
- Change from baseline to Week 12 (EOT) in the subscales scores (i.e., compulsive/obsessive, restraint, control) of the YBOCS-BE.
- Change from baseline to Week 6 (Visit 6) and to Week 12 (EOT) in the HAMD-17 total score.
- Change from baseline to Week 6 (Visit 6) and to Week 12 (EOT) in the HAMD-17 subitems 10 and 11.
- Change from baseline to Week 6 (Visit 6) and to Week 12 (EOT) in the HAMD-17 Maier-Philipp Subscale (MPS) score.
- Change from baseline to Week 12 (EOT) in EDE-Q7 global score and 3 subscales scores (i.e., dietary restraint, shape/weight overvaluation, body dissatisfaction).
- CGI-C score at Week 12 (EOT).
- PGI-C score at Week 12 (EOT).
- Change from baseline to Week 12 (EOT) in the CGI-S score.
- Change from baseline to Week 12 (EOT) in the PGI-S score.
- Change from baseline to Week 12 (EOT) in body weight.
- Change from baseline to Week 12 (EOT) in HbA1c^d.
- Improvement^e according to CGI-C score at Week 12 (EOT).

^a 'Number of BE episodes per week' is defined as the number of BE episodes in the applicable 14-day time interval divided by the total number of diary days, times 7.

^b 'Yes' is defined as BE episodes equal to 0.

^c 'Last 4 weeks of the treatment period' are defined as study days 57–84 [see Section 11.7].

^d Glycated hemoglobin.

^e Improvement according to CGI-C score is defined as CGI-C at Week 12 equal to "Much Improved" or "Very much improved". If CGI-C at Week 12 is missing, the study participant will be assumed to not have improved.

The above variables related to change from baseline will be summarized along with their observed values.

The YBOCS-BE is an interviewer-administered assessment developed to measure the severity of obsessive-compulsive symptoms in subjects with a diagnosis of obsessive-compulsive disorder modified to measure the BE thoughts and behaviors. The YBOCS-BE

ACT-539313		Statistical Analysis Plan
ID-082A201	Confidential	for Clinical Study Report
1 April 2022, page 30/60	Confidential	Version 3
		Doc No D-22.100

presents three subscales: compulsive/obsessive (Items #1, 2, 3, 6, 7 and 8), restraint (Items #4 and 9), and control (Items #5 and 10).

The HAMD-17 is an indicator of depression and anxiety. The HAMD-17 consists of 17 items, with most items providing a score that ranges between 'Absent' and 'Almost all the time'. The MPS sub-score combines items 1 (depressed mood), 2 (guilt), 7 (work and activities), 8 (psychomotor retardation), 9 (psychomotor agitation), and 10 (anxiety, psychic).

EDE-Q7 is a self-reported questionnaire containing 7 of the 28 questions from the EDE-Q about eating behaviors (Items #1, 3, 4, 22, 23, 25 and 26). The EDE-Q7 presents three subscales: dietary restraint (Items #1, 3 and 4), shape/weight overvaluation (Items #22 and 23), and body dissatisfaction (Items #25 and 26).

The CGI-C is a 1-item, 7-point scale that ranges from "Very much improved" to "Very much worse".

The PGI-C is a 1-item, 7-point scale that ranges from "Very much improved" to "Very much worse".

The CGI-S is a 1-item, 7-point scale that ranges from "Normal, not at all ill" to "Among the most extremely ill patients".

The PGI-S is a question concerning the overall severity of symptoms and impact that the study participant may have experienced due to his/her BE episodes over the 7 days preceding the PGI-S completion. It ranges from "No binge eating" to "Severe".

The exploratory efficacy endpoints will be tested at two-sided 5% significance level. No further Type I error control is applied; hence, these analyses are to be considered descriptive.

The MMRM [Section 6.1.3], will be fitted for:

- The change from baseline to Week 12 (EOT) in the number of BE episodes per week, with a covariate for the baseline number of BE episodes (rather than the number of BE days) per week.
- The change from baseline to Week 12 (EOT) in EDE-Q7 global score and 3 subscales, with a covariate for the time points limited to Week 4 (Visit 5), Week 8 (Visit 7), and Week 12 (EOT).
- The change from baseline to Week 12 (EOT) in the total score of the YBOCS-BE and in the subscales scores (i.e., compulsive/obsessive, restraint, control), with a covariate for the time points limited to Week 4 (Visit 5), Week 8 (Visit 7) and Week 12 (EOT).

ACT-539313		Statistical Analysis Plan
ID-082A201	Confidential	for Clinical Study Report
1 April 2022, page 31/60	Confidential	Version 3
		Doc No D-22.100

• The change from baseline to Week 6 (Visit 6) and to Week 12 (EOT) in the HAMD-17 total score, subitems 10 and 11, and MPS score, with a covariate for the time points limited to Week 6 (Visit 6) and Week 12 (EOT).

Absence of BE episodes will be analyzed using a logistic regression model with a factor for treatment group, sex and BMI category, and a covariate for the baseline number of BE episodes per week. For study participants who discontinued treatment prematurely, the outcome will be set to 'No absence'.

The CGI-C and PGI-C scores at Week 12 (EOT) will be compared between treatment groups using the Kruskal-Wallis test. Missing assessments at Week 12 will be imputed using last on-treatment observation carried forward.

The change from baseline to Week 12 (EOT) in the CGI-S score, PGI-S score, body weight and HbA1c will be analyzed using an ANCOVA model with a factor for treatment group and a covariate for baseline score. Missing assessments for CGI-S and PGI-S score at Week 12 will be imputed using last on-treatment observation carried forward.

The improvement according to CGI-C score at Week 12 (EOT) will be analyzed using a logistic regression model with a factor for treatment group.

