# Change from baseline to Week 12 in EDE-Q7 global score and 3 subscales

Changes from baseline in EDE-Q7 scores will be analyzed using a mixed model for repeated measurements as described for the primary endpoint, but with less time points.

# CGI-C score at Week 12

CGI-C scores will be compared between treatment groups using the Kruskal Wallis test.

# Improvement according to CGI-C at Week 12

This variable will be analyzed using a logistic regression model with a factor for treatment group. The relationship between improvement according to CGI-C at Week 12 and the primary efficacy outcome will be investigated.

# PGI-C score at Week 12

This variable will be analyzed using same methods as for CGI-C score at Week 12.

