14 APPENDICES

14.1 SAS[®] code for Mixed Model for Repeated Measures

This model is used, for example, for the main analyses of the primary and some exploratory efficacy endpoints. Assuming the data are in 'long' format (i.e., one row for each subject/visit) example SAS[®] statements for the primary endpoint analysis are:

proc mixed data=data; class SUBJID SEX BMIGR TRT VIS; model CHG = BASE SEX BMIGR TRT VIS TRT*VIS BASE*VIS / ddfm=kr residual outp=mixtable; lsmeans TRT*VIS / diff cl; repeated VIS / subject=SUBJID type=un; estimate 'ACT-539313 vs placebo at Week 12' TRT 1 -1 TRT*VIS 0 0 0 0 0 1 0 0 0 0 0 -1 / cl; ods output lsmeans=lsmeans estimates=estimates StudentPanel=StudentPanel FitStatistics=aic NObs=nobs;

run;

The dataset *data* includes baseline number of BE days (BASE) as well as changes (CHG) from baseline to Weeks 1–2, 3–4, 5–6, 7–8, 9–10, 11–12 (VIS) and BMI as categorical variable (BMIGR). Furthermore, TRT equals 1 and 2 for ACT-539313 and placebo, respectively. The model option *residual*, *outp=mixtable* and the statement *ods outout* are used to run the model diagnostic for the main analysis only.

If a sandwich estimator has to be used, the option *'empirical'* will be added to the proc mixed statement: proc mixed data=data empirical.

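### Read literally, SAP 6.3 adjusts YBOCS-BE, EDE-Q7 and HAMD-17 changes for baseline BE days rather than the scale's own baseline, which would cost precision in 12 exploratory outcomes

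*SAP*

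**What the plan says.** The model is brought into SAP 6.3 by cross-reference: "The MMRM [Section 6.1.3], will be fitted for" a list of four groups of endpoints. Section 6.1.3 fixes its content: "The analysis model will include the baseline number of BE days per week, treatment group (ACT-539313; placebo), sex, BMI category", time point, treatment by time point and baseline by time point.

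The four bullets of 6.3 then state what differs from that model:

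- BE episodes: "with a covariate for the baseline number of BE episodes (rather than the number of BE days) per week".
- EDE-Q7 global score and three subscales: "with a covariate for the time points limited to Week 4 (Visit 5), Week 8 (Visit 7), and Week 12 (EOT".
- YBOCS-BE total and three subscales: the same change of time points, and nothing on the baseline.
- HAMD-17 (Weeks 6 and 12): "HAMD-17 total score, subitems 10 and 11, and MPS score, with a covariate for the time points limited to Week 6 (Visit 6", again with nothing on the baseline.

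Protocol 9.2.4.2 handles EDE-Q7 in the same way: its scores "will be analyzed using a mixed model for repeated measurements as described for the primary endpoint, but with less time points". It leaves the other two scales to the SAP.

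SAP 14.1 introduces its code thus: "This model is used, for example, for the main analyses of the primary and some exploratory efficacy endpoints". It then gives an example for the primary endpoint in which BASE is baseline BE days. It has no instruction to change BASE for another endpoint. SAP 12.3, the place for clarifications, is marked as not applicable.

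**The concern.** The authors evidently saw that the cross-reference carries BE days with it, because they replaced that term for BE episodes. They made no such replacement for the three scales. A programmer who follows the text exactly would regress change in YBOCS-BE, EDE-Q7 or HAMD-17 on baseline BE days.

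The ANCOVA endpoints (CGI-S, PGI-S, body weight, HbA1c) are treated differently. For them 6.3 names the baseline score as covariate, and a code comment in 14.9 says that the baseline is to be swapped for each endpoint.

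A change score that is not adjusted for its own baseline is usually less precise, and a chance difference between arms on that scale stays in the estimate. Randomization is unstratified (protocol 6.1.3), so nothing else in the design balances these scales. The baselines are already collected at Visit 2.

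**Working it through.** **Count.** YBOCS-BE: total + 3 subscales = 4. EDE-Q7: global + 3 subscales = 4. HAMD-17: total, item 10, item 11, MPS = 4. The total is 12 outcomes. HAMD-17 is reported at Weeks 6 and 12, so there are 4 + 4 + 8 = 16 contrasts, each tested at two-sided 5%.

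**The plan's own figures.** The documents give no SD, correlation or power for these scales. The only sizing is for the primary endpoint, and it reproduces. For effect size 0.6 and 90% power, n per arm = 2(1.960 + 1.282)²/0.36 = 58.4, rounded up to 59, or 118 in total (protocol Table 5). Power at 120 is 78.2%, 90.8% and 97.0% for effect sizes 0.5, 0.6 and 0.7, against 78%, 91% and 97% in Table 6. The point below does not touch these figures.

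**Precision under the literal reading.** The symbols are:

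- baseline SD of the scale: 1
- Week 12 SD: k
- baseline to Week 12 correlation: ρ
- correlation of baseline BE days with the scale's baseline: r, with BE days related to the Week 12 score only through that baseline

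All three of k, ρ and r are assumptions. At Week 12 with complete data:

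- residual variance of change given own baseline = k²(1 − ρ²)
- residual variance of change given BE days = 1 + k² − 2ρk − r²(1 − kρ)²

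The second minus the first is (1 − r²)(1 − kρ)². The ratio of interval widths, BE days to own baseline, is therefore

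√{1 + (1 − r²)(1 − kρ)² / [k²(1 − ρ²)]}.

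With k = 1 and r = 0 this is √(2/(1 + ρ)). At ρ = 0.5 the variances are 1.00 and 0.75, and √(1.00/0.75) = 1.155.

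| k | r | ρ = 0.3 | ρ = 0.5 | ρ = 0.7 |
|---|---|---|---|---|
| 1.0 | 0 | 1.240 | 1.155 | 1.085 |
| 1.0 | 0.3 | 1.221 | 1.142 | 1.077 |
| 1.0 | 0.5 | 1.185 | 1.118 | 1.064 |
| 0.8 | 0 | 1.411 | 1.323 | 1.262 |
| 1.25 | 0 | 1.129 | 1.058 | 1.010 |
| 1.5 | 0 | 1.071 | 1.018 | 1.001 |

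The loss vanishes when the slope of Week 12 on baseline, kρ, equals 1. Within this set-up own baseline is never worse.

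A simulation with 60 per arm, sex and BMI category in the model, k = 1 and r = 0.3 gave standard-error ratios of 1.22, 1.14 and 1.08 for ρ = 0.3, 0.5 and 0.7, in line with the second row.

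**Illustration.** Take a difference of 0.5 SD, 60 per arm, k = 1, ρ = 0.5 and r = 0. Power is 88.5% with own baseline (residual SD √0.75 = 0.866) and 78.2% with BE days (residual SD 1).

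**The case against.** The strongest reply is that the SAP leaves the covariate unstated for these scales and does not choose BE days. That stands: no sentence says that YBOCS-BE, EDE-Q7 or HAMD-17 will be adjusted for baseline BE days. Own baseline is a plausible intent. SAP 11.4 defines baseline parameter by parameter, Table 7 sets a baseline window for each of the three scales, and wherever 6.3 names a baseline covariate for a change score it is the endpoint's own.

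Three stronger readings are tempting, and the documents do not support them.

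- A reader might infer that 14.1 defines BASE as BE days for the exploratory MMRMs. It describes the dataset of the primary-endpoint example, whose six diary intervals could not apply to the scales either. The same BE-days description appears under the ANCOVA code in 14.9, where 6.3 plainly requires the baseline score, so it looks like carried-over text and is weak evidence of intent. It also shows that a silent, correct update cannot be relied on: 14.6 describes BE days for a logistic model that 6.3 adjusts for baseline BE episodes.
- A reader might infer that regression to the mean biases the comparison. Under randomization it acts equally on both arms on average. Only precision and chance imbalance are at issue.
- A reader might turn the precision gain into extra participants, for example 1/0.85 = 1.18 to 1/0.65 = 1.54 times the sample. That needs equal SDs and assumed correlations. Equal SDs are doubtful for HAMD-17, because exclusion criterion 25 cuts its baseline off below 17. The trial is in any case sized on the primary endpoint alone.

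The outcomes are also exploratory and declared descriptive, without type I error control. That limits the consequence but does not remove the gap in the text.

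**Conclusion.** The point holds in conditional form. Followed exactly, SAP 6.3 and 6.1.3 give 12 exploratory change scores BE days, and not their own baseline, as the baseline term. Nothing in 14.1 or 12.3 corrects this, although own baseline may be intended.

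If it is programmed as written, confidence intervals are about 6% to 24% wider than with own-baseline adjustment. That assumes equal baseline and Week 12 SDs, ρ from 0.3 to 0.7 and r from 0 to 0.5. Over Week 12 to baseline SD ratios of 0.8 to 1.5, the range is roughly 0% to 41%. None of these inputs is in the documents.

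The treatment differences stay unbiased. The primary analysis, its alpha and the sample size are unaffected. Either way the text needs a correction: one reading probably wastes precision, and the other is not written down.

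**What to change.** In the EDE-Q7, YBOCS-BE and HAMD-17 bullets of SAP 6.3, add: *with the baseline value of the score analysed (total, subscale or item) and its interaction with time point in place of the baseline number of BE days per week*.

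In 14.1, add that BASE and BASE*VIS refer to the baseline of the endpoint analysed.

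The cost is one phrase in each of three bullets and one note to the code, settled before unblinding. No new data, visits or analyses are needed.
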